7.2 Secondary Efficacy Endpoints

- Change from baseline to Week 52 in patient-reported quality of life (SF-36 or Child Health Questionnaire);
- Change from baseline to Week 52 in cardiac MRI T2*;
- Change from baseline to Week 52 in serum ferritin.
- Detailed information on the statistical analyses of the SF-36 or CHQ data is in a separate SAP prepared by QualityMetric Inc..
- The changes from baseline to Week 52 in cardiac MRI T2* and serum ferritin will be compared between the two treatment groups, using an ANCOVA model including treatment variable as the

main factor, and overall average transfusional iron input during the study, baseline cardiac MRI T2* or serum ferritin, and stratification factors (disease category and transfusional iron input in the 3 months prior to baseline) as covariates. As with LIC, the 96.01% CI of the difference between the two treatment groups will be computed for both cardiac MRI T2* and serum ferritin. The cardiac MRI T2* data will be log-transformed before any statistical evaluation. Since cardiac MRI T2* will be measured at baseline, Week 26, and Week 52 as with LIC, the SAS codes for LIC data, with the exception of baseline MRI T2* instead of baseline LIC being included as the covariate, will be used for cardiac MRI T2* data as well.

- The following SAS codes of MIXED procedure will be used to produce the differences in Least Squares (LS) Mean of change in serum ferritin at Months 3, 6, 9, and 12 between Ferriprox and deferoxamine groups and the corresponding 96.01% confidence intervals.

```
proc mixed data=SF;
  class patient treat disease prior_iron month;
  model SF_change = treat overall_iron base_SF disease prior_iron
    month treat*month /
    noint solution ddfm=kr;
  repeated month / subject=patient(treat) type=ar(1);
  lsmeans treat*month;
  estimate 'Ferriprox - Deferoxamine at Month 3' treat -1 1
    treat*month -1 0 0 0 1 0 0 0 / cl alpha=0.0399;
  estimate 'Ferriprox - Deferoxamine at Month 6' treat -1 1
    treat*month 0 -1 0 0 0 1 0 0 / cl alpha=0.0399;
  estimate 'Ferriprox - Deferoxamine at Month 9' treat -1 1
    treat*month 0 0 -1 0 0 0 1 0 / cl alpha=0.0399;
  estimate 'Ferriprox - Deferoxamine at Month 12' treat -1 1
    treat*month 0 0 0 -1 0 0 0 1 / cl alpha=0.0399;
run;
```

Definition of the variables in the statistical model:

SF_change : Change in SF from baseline to Week 5
 treat : Ferriprox or Deferoxamine
 month : Duration of treatment in month
 overall_iron : Overall total transfusional iron input (mg/kg/day) during the study
 base_LIC : LIC at baseline
 disease : Sickle cell disease or other anemias
 prior_iron : transfusional iron input in 3 months prior to baseline (≤ 0.3 mg/kg/day or > 0.3 mg/kg/day)

7.3 Trend Analysis for LIC, cardiac MRI T2*, and Serum Ferritin

The longitudinal data of LIC, cardiac MRI T2*, and serum ferritin will be analyzed for time trend by using PROC MIXED procedure in SAS. The observed data of LIC, log-transformed cardiac MRI T2*, and serum ferritin will be used in this analysis. The following two statistical models will be fitted:

- Model 1: Efficacy value = Intercept + Treatment + Time + Treatment \times Time
- Model 2: Efficacy value = Intercept + Treatment + Time

Treatment will be treated as a categorical variable, and Time will be the time in month at each time point. Model 1 is the full model with the main effect of Treatment and Time, and the interaction effect of Treatment \times Time. Model 2 is the reduced model with the main effect of Treatment and Time without the interaction term. If the interaction of Treatment \times Time in Model 1 is not significant ($p > 0.05$), the reduced Model 2 will be used as the final model for trend analysis.

The following SAS codes will be used:

```
proc mixed data=efficacy_data;
  class patient treat;
  model measure = treat month treat*month / solution ddfm=kr;
  repeated / subject=patient(treat) type=ar(1);
run;
```

Definition of the variables in the statistical model:

measure: LIC or log-transformed cardiac MRI T2*, or SF
treat : Ferriprox or Deferoxamine
month : Duration of treatment in month

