		Treatment		
	Deferiprone	Deferoxamine		
N	xxx	xxx		
		Mean ± SD (Min, Max)	Mean ± SD (Min, Max)	P-value (T-test)
Weight (kg)	xx.x ± xx.x (xx, xx)	xx.x ± xx.x (xx, xx)	0.xxxx	
Height (cm)	xxx.x ± xxx.x (xxx, xxx)	xxx.x ± xxx.x (xxx, xxx)	0.xxxx	

§For patients who had separate screening and baseline visits, height was measured only at screening

Data source: 16.2.7 Listing of vital signs including height and weight

Table 14.2.1.1 LIC at each assessment

		Treatment		
		Deferiprone	Deferoxamine	
N		xxx	xxx	P-value (T-test)
	Visit	Mean \pm SD (Min, Max)	Mean \pm SD (Min, Max)	
LIC (mg/g dw)	Baseline	xx.x \pm xx.x (xx.x, xx.x)	xx.x \pm xx.x (xx.x, xx.x)	0xxxx
	Month 6	xx.x \pm xx.x (xx.x, xx.x)	xx.x \pm xx.x (xx.x, xx.x)	0xxxx
	Month 12	xx.x \pm xx.x (xx.x, xx.x)	xx.x \pm xx.x (xx.x, xx.x)	0xxxx

Data source: 16.2.13 Listing of LIC

Table 14.2.1.2 Change in LIC at each follow-up assessment

		Treatment		
Test	Visit	Deferiprone	Deferoxamine	
N		xxx	xxx	P-value (T-test)
Change in LIC (mg/g dw) Mean \pm SD (Min, Max)	Month 6	xx.x \pm xx.x (xx.x, xx.x)	xx.x \pm xx.x (xx.x, xx.x)	0xxxx
	Month 12	xx.x \pm xx.x (xx.x, xx.x)	xx.x \pm xx.x (xx.x, xx.x)	0xxxx

Data source: 16.2.13 Listing of LIC

Table 14.2.1.3 LS Means of change in LIC from ANCOVA model at each follow-up assessment

		Treatment			
		Deferiprone	Deferoxamine	Deferiprone minus Deferoxamine	96.01% C.I.
N		xxx	xxx	xxx	
	Visit	LS Mean \pm SE	LS Mean \pm SE	LS Mean \pm SE	
LIC (mg/g dw)	Month 6	xx.x \pm xx.x	xx.x \pm xx.x	xx.x \pm xx.x	(xx.x, xx.x)
	Month 12	xx.x \pm xx.x	xx.x \pm xx.x	xx.x \pm xx.x	(xx.x, xx.x)

Data source: 16.2.13 Listing of LIC

Table 14.2.1.4 Trend analysis for LIC over time

	Deferiprone	Deferoxamine	Deferiprone minus Deferoxamine	P-value
Slope: Mean \pm SE	xx.x \pm xx.x	xx.x \pm xx.x	xx. x \pm xx.x	0.xxxx

Data source: 16.2.13 Listing of LIC

Table 14.2.1.5 Success rate in LIC based on the submission of Exjade's NDA.

	Treatment		
	Deferiprone	Deferoxamine	P-value (Fisher's exact test)
Success rate	xx.x %	xx.x%	0.xxxx

Data source: 16.2.13 Listing of LIC

Table 14.2.2.1 Cardiac MRI T2* at each assessment

		Treatment		
		Deferiprone	Deferoxamine	
N		xxx	xxx	P-value (T-test)
	Visit	Mean \pm SD (Min, Max)	Mean \pm SD (Min, Max)	
Cardiac MRI T2* (ms)	Baseline	xx.x \pm xx.x (xx.x, xx.x)	xx.x \pm xx.x (xx.x, xx.x)	0.xxxx .
	Month 6	xx.x \pm xx.x (xx.x, xx.x)	xx.x \pm xx.x (xx.x, xx.x)	0.xxxx
	Month 12	xx.x \pm xx.x (xx.x, xx.x)	xx.x \pm xx.x (xx.x, xx.x)	0.xxxx

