Data source: 16.2.14 Listing of cardiac MRI T2*

Table 14.2.2.2 Change in cardiac MRI T2* at each follow-up assessment

		Treatment			
Test		Visit	Deferiprone	Deferoxamine	
N			xxx	xxx	P-value (T-test)
Change in cardiac MRI T2* (ms) Mean \pm SD (Min, Max)	Month 6	xx.x \pm xx.x (xx.x, xx.x)	xx.x \pm xx.x (xx.x, xx.x)	0.xxxx	
	Month 12	xx.x \pm xx.x (xx.x, xx.x)	xx.x \pm xx.x (xx.x, xx.x)	0.xxxx	

Data source: 16.2.14 Listing of cardiac MRI T2*

Table 14.2.2.3 LS Means of change in cardiac MRI T2* from ANCOVA model at each follow-up assessment

		Treatment			
		Deferiprone	Deferoxamine	Deferiprone minus Deferoxamine	96.01% C.I.
N		Xxx	xxx	xxx	
	Visit	LS Mean \pm SE	LS Mean \pm SE	LS Mean \pm SE	
Cardiac MRI T2* (ms)	Month 6	xx.x \pm xx.x	xx.x \pm xx.x (xx.x, xx.x)	(xx.x, xx.x)	(xx.x, xx.x)
	Month 12	xx.x \pm xx.x	xx.x \pm xx.x (xx.x, xx.x)	(xx.x, xx.x)	(xx.x, xx.x)

Data source: 16.2.14 Listing of cardiac MRI T2*

Table 14.2.2.4 Trend analysis for cardiac MRI T2* over time

	Deferiprone	Deferoxamine	Deferiprone minus Deferoxamine		P-value
Slope: Mean \pm SE	xx.x \pm xx.x	xx.x \pm xx.x	xx. x \pm xx.x	0.xxxx	

Data source: 16.2.14 Listing of cardiac MRI T2*

Table 14.2.3.1 Serum ferritin each assessment

		Treatment		
		Deferiprone	Deferoxamine	
N		xxx	xxx	P-value (T-test)
	Visit	Mean ± SD (Min, Max)	Mean ± SD (Min, Max)	
Serum Ferritin (µg/L)	Baseline	xx.x ± xx.x (xx.x, xx.x)	xx.x ± xx.x (xx.x, xx.x)	0xxxx
	Month 3	xx.x ± xx.x (xx.x, xx.x)	xx.x ± xx.x (xx.x, xx.x)	0xxxx
	Month 6	xx.x ± xx.x (xx.x, xx.x)	xx.x ± xx.x (xx.x, xx.x)	0xxxx
	Month 9	xx.x ± xx.x (xx.x, xx.x)	xx.x ± xx.x (xx.x, xx.x)	0xxxx
	Month 12	xx.x ± xx.x (xx.x, xx.x)	xx.x ± xx.x (xx.x, xx.x)	0xxxx

Data source: 16.2.21 Listing of serum ferritin

Table 14.2.3.2 Change in serum ferritin at each follow-up assessment

		Treatment		
Test	Visit	Deferiprone	Deferoxamine	
N		xxx	xxx	P-value (T-test)
Change in serum ferritin (µg/L) Mean ± SD (Min, Max)	Month 3	xx.x ± xx.x (xx.x, xx.x)	xx.x ± xx.x (xx.x, xx.x)	0xxxx
	Month 6	xx.x ± xx.x (xx.x, xx.x)	xx.x ± xx.x (xx.x, xx.x)	0xxxx
	Month 9	xx.x ± xx.x (xx.x, xx.x)	xx.x ± xx.x (xx.x, xx.x)	0xxxx
	Month 12	xx.x ± xx.x (xx.x, xx.x)	xx.x ± xx.x (xx.x, xx.x)	0xxxx

Data source: 16.2.21 Listing of serum ferritin

Table 14.2.3.3 LS Means of change in serum ferritin from ANCOVA model at each follow-up assessment

		Treatment			
		Deferiprone	Deferoxamine	Deferiprone minus Deferoxamine	96.01% CI
N		Xxx	xxx	xxx	
	Visit	LS Mean ± SE	LS Mean ± SE	LS Mean ± SE	

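### SAP 7.3 makes a common-slope model final whenever treatment-by-time has p > 0.05, so in that branch the final model cannot supply the slope difference, SE and p-value that the three trend tables require

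*SAP*

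**What the plan says.** SAP 7.3 applies to observed LIC, log-transformed cardiac T2* and serum ferritin. It announces that "The following two statistical models will be fitted":

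- **Model 1:** "Model 1 is the full model with the main effect of Treatment and Time, and the interaction effect of Treatment" by time.
- **Model 2:** "Model 2 is the reduced model with the main effect of Treatment and Time without the interaction term".

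Time is continuous: "Time will be the time in month at each time point", and month is absent from the CLASS statement, so its coefficient is a slope. When the interaction has p > 0.05, "the reduced Model 2 will be used as the final model for trend analysis". The only code given is for Model 1: "model measure = treat month treat*month / solution ddfm=kr".

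The results go into three shells in SAP section 17: "Table 14.2.1.4 Trend analysis for LIC over time", "Table 14.2.2.4 Trend analysis for cardiac MRI T2* over time" and Table 14.2.3.4 for serum ferritin. Each has a single row for the slope (mean and SE), with columns for deferiprone, deferoxamine, their difference and a p-value. There is no shell for a common slope, and no statement of which model fills the table when Model 2 is final.

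The protocol (11.4.1.3) asks only that the longitudinal data also be analysed for time trend with an appropriate mixed model. It contains no rule for dropping the interaction.

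**The concern.** The selection rule and the tables pull in opposite directions. The tables exist to compare slopes between arms. The rule removes the parameter that measures that comparison whenever it fails a 5% test. A reader of the report would then see either no estimate of the slope difference or a zero that was imposed and not estimated.

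Failure to reject equal slopes may reflect limited precision as easily as similarity, and without an interval the reader cannot tell which. When the interaction is kept, it has been kept because it was large relative to its error, so the retained estimates are on average too far from zero. At stake is the interpretability of one supportive table per measure.

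**Working it through.** The documents give no power or effect size for the trend analysis, so there is no planned figure to reproduce. The check is structural, followed by an illustration.

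**Structure.** Code treatment as 0 for deferoxamine and 1 for deferiprone.

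- Model 1: the slopes are b_time and b_time + b_int. The difference is b_int, with an SE and a p-value.
- Model 2: b_int is absent. Both slopes are b_time, and the difference is b_time − b_time = 0, with no SE and no test.

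Model 2's remaining treatment term is an average difference in level over the visits, which is not a difference in trend. The final model therefore gives the same slope for both arms and nothing for the SE of the difference or the p-value.

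**Illustration for LIC.** Inputs from the SAP's sample size text (before section 3.3): 142 Ferriprox and 71 deferoxamine patients, SD 4.0 mg/g dw. Assumptions added here: complete data, SD 4 applied to the 12-month change, and baseline, Month 6 and Month 12 all in the trend model.

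SE of the 12-month difference = 4 × √(1/142 + 1/71) = 0.581 mg/g dw, or 0.581/12 = 0.048 per month.

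An observed difference smaller in size than 1.96 × 0.581 = 1.14 mg/g dw per year (0.095 per month) leads to Model 2 and is replaced by 0.

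For a true difference d, P(Model 2) = Φ(1.96 − d/0.581) − Φ(−1.96 − d/0.581):

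| True difference d (mg/g dw per year) | d/SE | P(Model 2 final) |
|---|---|---|
| 0 | 0 | 95% |
| 0.5 | 0.86 | 86% |
| 1.0 | 1.72 | 59% (0.595) |
| 1.5 | 2.58 | 27% |
| 2.0 | 3.44 | 7% |

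**Check by simulation.** Generalised least squares with AR(1) errors, visits at 0, 6 and 12 months, an assumed correlation of 0.7 between adjacent visits, and 4,000 runs per scenario. Model 2 was selected in 94.4%, 58.9%, 27.2% and 6.5% of runs at d = 0, 1, 1.5 and 2. The average 12-month differences were:

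| True d | Model 1 always | Select, then report (0 if dropped) | Retained runs only |
|---|---|---|---|
| 1.0 | 1.01 | 0.64 | 1.56 |
| 2.0 | 2.01 | 1.95 | 2.09 |

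Always reporting Model 1 is unbiased. The rule shrinks the reported difference on average and inflates it in the runs where it survives.

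**Subgroups.** The note to SAP 14.2 calls for similar tables in SCD and non-SCD patients. The SAP gives 119/59 SCD patients, which leaves 23/12 non-SCD. If the rule is applied there with the same SD:

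- SCD: SE = 4 × √(1/119 + 1/59) = 0.637; a true 1 mg/g dw is dropped in about 65% of trials.
- Non-SCD: SE = 4 × √(1/23 + 1/12) = 1.424; a true 2 mg/g dw is dropped in about 71%.

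**The case against.** The strongest reply is that this is a reporting ambiguity in a supportive analysis. Several parts of it stand.

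- **The numbers exist.** Both models are fitted, and the rule cannot be applied without Model 1's interaction p-value. SAP 17 also allows tables to differ from the shells. A reader might infer that the tables are impossible to fill. The documents do not support that: the cells cannot come from the model named as final, but they can come from Model 1. What is missing is an instruction to report it, and the instruction that is present points to the other model.
- **The interaction test is valid.** It is the ordinary Model 1 test at 0.05, and dropping the term afterwards does not change its false-positive rate. So it would go too far to say that no error measure here is valid. The defect is narrower: estimates read after selection are biased and lack nominal coverage, and the p > 0.05 branch gives no interval for the difference.
- **Non-inferiority does not rest on this.** A reader might infer that a non-significant interaction is being used to support non-inferiority. It is not. That decision uses the 96.01% interval for the Week 52 LIC difference in SAP 7.1, from a model that always keeps treatment by month.
- **The between-arm comparison is reported elsewhere.** Tables 14.2.1.3, 14.2.2.3 and 14.2.3.3 give adjusted differences with 96.01% intervals at Months 6 and 12 for LIC and T2*, and at Months 3, 6, 9 and 12 for ferritin, whatever the trend analysis does.
- **The figures are illustrative.** The 213 patients include withdrawals, while the trend uses observed data. No SD is given for T2* or ferritin, and the 2 mg/g dw margin is never applied to slopes.

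None of this removes the mismatch: followed literally, the rule fixes the tabulated difference at zero.

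**Conclusion.** The point holds as a faulty rule in a supportive analysis. When the interaction has p > 0.05, the designated final model fixes the slope difference at 0 and cannot supply the entries in Tables 14.2.1.4, 14.2.2.4 and 14.2.3.4. When p ≤ 0.05, Model 1 fills them. The first branch is the expected one under the SAP's own planning assumption of no real difference in efficacy: about 95% of trials if the slopes are equal.

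The LIC probabilities rest on complete data and SD 4 for the 12-month change. Missing data at the same SD would raise the SE and make Model 2 more likely at any given true difference. The structural argument applies equally to T2* and ferritin, but the documents allow no probabilities for them. The point should be corrected, but it bears on no endpoint conclusion.

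**What to change.** In SAP 7.3, delete the rule that selects Model 2. State that Model 1 is the trend model in all cases and that its two slopes, their difference, SE, confidence interval and p-value are reported whatever the interaction p-value. State the confidence level for the interval. Model 2 can be removed or kept as a labelled descriptive fit.

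Add a confidence interval column to the three trend shells, which now have SE and p-value only, and carry the same change into the SCD and non-SCD versions.

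The cost is a few lines of SAP text and one table column. The Model 1 code already exists; requesting the slope estimates and interval is a small addition. No new data or patients are needed, and the primary and secondary analyses do not change.

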5. HANDLING OF MISSING DATA

In the efficacy analyses, for patients who were terminated from the study prior to Month 12, if their last efficacy measures were obtained within 30 days of Month 12, the data obtained will be treated as the Month 12 data. For early termination that occurred outside this window, the last observation carried forward (LOCF) method will be used to fill the missing data when the early termination was not caused by worsening of disease conditions or inadequate efficacy of the drug. For early termination due to worsening

of disease conditions or inadequate efficacy of the drug, as judged by assessing the AE log, the “worst value” method will be used. That is, the worst value of all patients from the corresponding treatment group will be used to impute the missing data at that time point. For missing data due to missed visit, the LOCF method will be used to fill the void.

For safety data analysis, no imputation will be performed on the missing data, and analysis will be based on observed cases (OC).

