7.1 Primary Efficacy Endpoint

Primary efficacy endpoint is the change from baseline to Week 52 in LIC. Primary efficacy endpoint will be compared between the two treatment groups using an analysis of covariance (ANCOVA) model including treatment variable as the main factor, and overall average transfusional iron input during the study, baseline LIC, and stratification factors (disease category and transfusional iron input in the 3 months prior to baseline) as covariates. The 96.01% $(1 - \alpha)$, where $\alpha = 0.0399$ based on the Pocock’s α spending function for interim analysis) confidence interval (CI) of the difference (Ferriprox minus deferoxamine) in change of LIC from baseline to Week 52 (i.e., Week 52 minus baseline) between the two treatment groups

will be computed. For the demonstration of non-inferiority, the upper limit of the 96.01% CI should be no more than 2 mg/g dw.

The following SAS codes of MIXED procedure will be used to produce the differences in Least Squares (LS) Mean of change in LIC at Month 6 and Month 12 between Ferriprox and deferoxamine groups and the corresponding 96.01% confidence intervals. In the mixed model, AR (1) (autoregressive of order 1) will be used for the covariance structure, and Kenward and Roger's method will be used to estimate the denominator degrees of freedom (SAS model statement option, DDFM = KR).

```

proc mixed data=LIC;
  class patient treat disease prior_iron month
  model LIC_change = treat overall_iron base_LIC disease prior_iron
    month treat*month / noint solution ddfm=kr;
  repeated month / subject=patient(treat) type=ar(1);
  lsmeans treat*month;
  estimate 'Ferriprox - Deferoxamine at Month 6' treat -1 1
    treat*month -1 0 1 0 / cl alpha=0.0399;
  estimate 'Ferriprox - Deferoxamine at Month 12' treat -1 1
    treat*month 0 -1 0 1 / cl alpha=0.0399;
run;

```

Definition of the variables in the statistical model:

LIC_change : Change in LIC from baseline to Week 5
 treat : Ferriprox or Deferoxamine
 month : Duration of treatment in month
 overall_iron : Overall total transfusional iron input (mg/kg/day) during the study
 base_LIC : LIC at baseline
 disease : Sickle cell disease or other anemias
 prior_iron : transfusional iron input in 3 months prior to baseline (≤ 0.3 mg/kg/day or > 0.3 mg/kg/day)

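### The trend-model code in SAP 7.3 names no visit effect, so an interior missed visit without a placeholder row is given the wrong AR(1) lag; the effect on slope standard errors is modest

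*SAP*

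**What the plan says.** SAP 7.3 models each efficacy value on treatment, time and, in Model 1, their interaction. On the data it says: "The observed data of LIC, log-transformed cardiac MRI T2*, and serum ferritin will be used in this analysis". On time it says: "Time will be the time in month at each time point". Month is therefore a continuous regressor, and the CLASS statement lists only "class patient treat". The covariance line is "repeated / subject=patient(treat) type=ar(1"), with nothing between the keyword and the slash. If the interaction has p > 0.05, the reduced Model 2 becomes the final model.

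The LIC change model in SAP 7.1 has "repeated month / subject=patient(treat) type=ar(1") instead. The ferritin change model in SAP 7.2 also names month in REPEATED, and its CLASS list is "class patient treat disease prior_iron month". SAP 7.2 reuses the LIC code for cardiac T2*.

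SAP section 5 expects missed visits and gives a rule for the efficacy analyses: "For missing data due to missed visit, the LOCF method will be used to fill the void". Because SAP 7.3 specifies observed data, that rule does not fill gaps in the trend models. The SAP does not describe the layout or sort order of the trend data set.

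**The concern.** AR(1) makes the correlation between two records depend on how many steps separate them. With no repeated effect, PROC MIXED counts steps by record order within the subject. If a missed visit has no row, the visits on either side of it become neighbours and receive the one-step correlation instead of the two-step correlation.

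This looks like an oversight. Month had to leave the CLASS list so that a slope could be fitted, and no classification copy of the visit replaced it in REPEATED.

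At stake are the slope standard errors and p-values in Tables 14.2.1.4, 14.2.2.4 and 14.2.3.4, and the interaction test that decides which trend model is reported.

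**Working it through.** The documents give no numerical result for the trend models, so there is no figure to reproduce. The code was checked by reading it, not by running SAS. The size of the effect was computed from large-sample theory.

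**Inputs from the documents**
- LIC and cardiac T2*: baseline, Weeks 26 and 52, so one interior visit (Protocol synopsis, Schedule of Study Procedures).
- Serum ferritin: baseline, Weeks 12, 26, 40 and 52, so three interior visits (same place).
- Arms of 142 and 71 (SAP sample-size text on the 213 patients).

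**Assumptions, not in the documents**
- One-visit correlation ρ from 0.5 to 0.9.
- 5% or 20% of interior visits missed, at random and at the same rate in both arms.
- Baseline is included as month 0; nominal months are 0, 6, 12 for LIC and 0, 3, 6, 9, 12 for ferritin.
- Missed visits have no row.

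**Step 1: the lag error.** Two records two visits apart should have correlation ρ². At a given ρ, record order assigns them ρ instead:

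| ρ | by visit (ρ²) | by record order |
|---|---|---|
| 0.5 | 0.25 | 0.50 |
| 0.7 | 0.49 | 0.70 |
| 0.9 | 0.81 | 0.90 |

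**Step 2: what the model fits.** One variance and one correlation are estimated from all patients. For missingness pattern k with probability p, let S be the true covariance, ρ^|difference in visit number|, and W the fitted one, σ²r^|difference in record order|. The fitted values minimise Σ p·[log|W| + tr(W⁻¹S)]. For LIC at ρ = 0.7 with 20% missed, the fitted r is 0.677.

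**Step 3: standard errors.** With A = ΣX′W⁻¹X and B = ΣX′W⁻¹SW⁻¹X, summed over patients, the model-based variance is A⁻¹ and the true variance is A⁻¹BA⁻¹. The ratio q is the model-based SE over the true SE of the treatment-by-time slope difference. The size of the nominal 5% test is 2·[1 − Φ(1.96q)].

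| Measure | Interior visits missed | q, ρ = 0.5 | q, ρ = 0.7 | q, ρ = 0.9 | Test size, ρ = 0.5 to 0.9 |
|---|---|---|---|---|---|
| LIC | 0% | 1.000 | 1.000 | 1.000 | 5.0% |
| LIC | 5% | 0.987 | 0.980 | 0.972 | 5.3–5.7% |
| LIC | 20% | 0.959 | 0.941 | 0.923 | 6.0–7.1% |
| Ferritin | 0% | 1.000 | 1.000 | 1.000 | 5.0% |
| Ferritin | 5% | 0.986 | 0.976 | 0.960 | 5.3–6.0% |
| Ferritin | 20% | 0.952 | 0.920 | 0.878 | 6.2–8.5% |

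Example: for ferritin with ρ = 0.9 and 20% missed, 1.96 × 0.878 = 1.72, so the size is 2·[1 − Φ(1.72)] ≈ 8.5%. Cardiac T2* has the LIC visit schedule, so the LIC rows apply to it on the log scale.

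**Step 4: with the visit indexed.** Under the same assumptions W has the same form as S, q is 1.00 throughout and the test has its nominal size.

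**Step 5: a different truth.** If correlation is exchangeable at 0.7, with 20% of Week 26 scans missed, q for LIC is 1.19 as written and 1.28 with the visit indexed. Most of that excess comes from choosing AR(1), not from the missing visit effect. With complete LIC data the generalised least-squares slope uses only the first and last scan, so q = √[(1 − 0.7²)/(1 − 0.7)] = √1.7 ≈ 1.30 under either coding.

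**The case against.** The strongest objection is that the code is wrong only under conditions that the SAP leaves open. There must be a gap between two observed visits, and the missed visit must have no row. Dropout with nothing observed afterwards leaves record order correct. A row with a missing response, kept in visit order, preserves the positions. Observed data means that values are not imputed; it does not say that rows are deleted. This stands. The supported statement is that the code relies on a data layout that the SAP never specifies.

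A reader might infer a much larger effect from a single patient. At a fixed correlation r, the variance of one patient's baseline-to-Week-52 change is understated by (1 − r²)/(1 − r) = 1 + r, or 1.5- to 1.9-fold for r from 0.5 to 0.9. That is not the error in the reported analysis. The trend tables report slopes and a slope difference from one model fitted to all patients, and most patients may have no gap.

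A reader might also infer that the standard errors are always too small. The documents give no correlation structure. The stated direction holds if AR(1) by visit is true; under exchangeable correlation the standard error is too large, and indexing the visit moves it further from the truth. This also stands, but it questions the choice of AR(1). The point here is that the code may not carry out the structure that the SAP chose.

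Nor do the documents show whether SAS would issue a warning, and this was not tested.

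**Conclusion.** The point holds as a conditional coding fault with modest effect. If missed visits have no row, interior gaps are misaligned. If AR(1) by visit is true, with the correlations and random missingness assumed above, the slope-difference standard error is about 1–4% too small at 5% missed and 4–12% too small at 20% missed. The interaction test's size rises to about 5.3–6.0% and 6.0–8.5%, which can affect the choice between Model 1 and Model 2. With no interior gaps there is no effect.

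A reader might take this as a threat to the trial's main conclusion. It is not: the non-inferiority comparison uses the SAP 7.1 model, and that model and the secondary change models name month. Protocol 11.4.1.3 presents the time-trend analysis as an addition to those comparisons. The correction is desirable rather than essential.

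**What to change.** In SAP 7.3, create a classification copy of the scheduled visit, write `class patient treat visit;` and `repeated visit / subject=patient(treat) type=ar(1);`, and keep month continuous in MODEL. Record positions then no longer depend on row order or placeholder rows, and the code matches the practice in SAP 7.1 and 7.2.

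Early-termination assessments can fall between scheduled visits. If they enter the trend models at their actual times, use `type=sp(pow)(month)`, which bases correlation on elapsed time, and say so in the text.

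The cost is a derived variable and small edits to the CLASS and REPEATED statements. No new data are needed, and the fixed effects stay the same.
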